2.1.2. Omnipod Horizon™ ACE Pump

The Pod component of the Omnipod Horizon™ System is similar to the Omnipod® DASH ACE Pump cleared under K191679. Compared to the DASH ACE Pump (K191679), the Horizon™ ACE Pump (Pod) has additional software to optimize communication to accept inputs from the iCGM (initially the Dexcom G6) and the Horizon™ Controller. The insulin delivery mechanism and the patient and fluid contacting components are identical to the DASH Pod.

The Pod is a lightweight, self-adhesive device that the user fills with U-100 rapid-acting insulin and wears directly on their body. The Pod delivers insulin into the user's body through a small flexible tube, called a cannula, based on the commands from the compatible controller. In the Omnipod Horizon™ System, the Pod will house the MPC algorithm and communicate directly with the iCGM and the Horizon App. The algorithm commands the Pod's insulin delivery in the form of micro-boluses based on predicted glucose values. As with the cleared Omnipod® DASH System, the Pod of the Omnipod Horizon™ System will come pre-packaged in a sterile container with a fill needle and a fill syringe. **Figure 2** below is a representation of the Pod.

[figure not shown]

Figure 2: The Pod of the Omnipod Horizon™ ACE pump

2.1.3. iCGM

The third component of the Omnipod Horizon™ System is the iCGM. The Omnipod Horizon™ System will be interoperable with a compatible iCGM, currently the Dexcom G6 Continuous Glucose Monitoring System (K191450). The Omnipod Horizon™ Pod will communicate with the Dexcom G6 via Bluetooth Low Energy (BLE). Glucose values from the Dexcom transmitter will be sent to the MPC algorithm residing on the Pod and used in insulin dosing adjustments. The glucose values from the Dexcom transmitter will be sent independently to the Dexcom App on the controller.

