Subjects who meet all eligibility criteria and have completed all screening assessments will continue to enrollment. A subject is enrolled in the study upon placement of the first study CGM. Subjects that do not meet the eligibility criteria will not continue in the study and will be considered screen failures.

If for any reason a subject is no longer eligible for the study after the standard therapy phase has commenced but prior to the commencement of the hybrid closed-loop phase, the subject will not continue in study. No additional study assessments will be required. The reason for study exit will be clearly documented.

8 STANDARD THERAPY - PHASE 1

The standard therapy phase will commence after all standard therapy assessments are completed per **Visit 2** – see Table 1: Schedule of Assessments for Phase 1 and Phase 2.

During the standard therapy phase, subjects and/or parents/guardians will be asked to perform the following:

- Manage their diabetes at home per their usual routine
- Administer meal boluses per their usual dosing routine
- Change their sensor if a sensor fails, or as needed
- Calibrate their CGM, if required, per the manufacturer's instructions
- Monitor their capillary blood glucose (BG) per usual routine
- Give meal boluses. The timing of the bolus delivery will be per each subject's typical dosing routine.

Extending standard therapy past 14-days will not constitute a protocol deviation unless standard therapy extends past 30-days. If subjects extend beyond the 14-days, the most recent 14-days of data will be used in the endpoint analysis if the data meets the criteria defined for CGM use and data availability.

The standard therapy phase will be customized depending on the following subject profile:

- Current Dexcom G6 users
- Non-G6 users
- Pump Naïve users

Current Dexcom G6 Users

Current Dexcom G6 users will be required to participate in the assessments required as part of standard therapy (ST1/Visit 2) but may be exempt from wearing the study CGM for 14-days if the following criteria are met:

- Willing to provide 14-days of CGM data from the past 30-days
- Meet the success criteria of 80% CGM use during any consecutive 14-days in the past 30-days
- Must have $\geq 2,016$ CGM values during the 14-days

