If exemption criteria are not met, subjects and/or parents/guardians may choose to continue to collect data until they meet the criteria or will be required to participate in the entire 14-day standard therapy phase consistent with the requirements for non-G6 users.

Subjects deemed exempt from wearing the study CGM for 14-days will be immediately eligible to commence the hybrid closed-loop phase starting at Visit 4.

Non-G6 Users

All non-G6 users will be required to participate in the entire 14-day standard therapy phase. At the commencement of the standard therapy phase, subjects will be dispensed a CGM receiver that will be blinded and all user settable CGM alerts will be turned off. The device will record continuous glucose information over the 14-day period.

Pump Naïve Users

Subjects who are naïve to pump therapy will have the opportunity to participate in a saline trial during the standard therapy phase. A saline trial consists of wearing a cleared Omnipod® DASH System with the Pod filled with saline to simulate pump therapy. This would enable subjects and/or parents/guardians to familiarize themselves with the basic concepts of basal and bolus insulin delivery as well as provide the experience of wearing an on-body device prior to their participation in the hybrid closed-loop phase, if they choose to do so. This is optional and not required. If a pump naïve subject is also a current G6 user that meets the criteria as stated above, the subject will complete the saline trial prior to enrollment in the study.

8.1 Visit 2

Visit 2 represents the commencement of the standard therapy phase. All scheduled assessments will be performed according to Table 1: Schedule of Assessments for Phase 1 and Phase 2. This visit will include:

- Review of concomitant medications
- Average total daily insulin (approximately over the past 7 days)
- Average total daily basal insulin (approximately over the past 7 days)
- Average total daily bolus insulin (approximately over the past 7 days)
- Review of pump settings/MDI dosing
- Assessment of AEs
- Completion of questionnaires (see Table 2: Questionnaires):
 - WHO-5
 - Used to measure current mental well-being
 - DTSQs Parent
 - Used to measure satisfaction with diabetes treatment regimens
 - P-PAID-Child
 - Measures diabetes-related burden
 - Hypoglycemia Confidence Scale
 - Used to measure hypoglycemia unawareness, hypoglycemia frequency, severity and impact
 - PSQI

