12.3.2 Reportable Adverse Events

Adverse events will be assessed on an ongoing basis throughout the study. Adverse event reporting will begin at the start time of the standard therapy phase (i.e., insertion of the CGM sensor) and continue through the hybrid closed-loop Phase 2 and 3 until the subject's participation has ended. All reported adverse

events must be followed until resolution, or until the AE has stabilized, or until the study has been completed.

Pre-existing medical conditions or symptoms observed prior to the start time of the standard therapy phase will not be recorded as an AE and should be collected in the subject's medical history. In the event there is a change (i.e., worsening) in the pre-existing medical condition or symptoms after enrollment meeting the criteria of a reportable adverse event, then an AE must be reported.

For this protocol, a reportable adverse event includes any untoward medical occurrence that meets one of the following criteria:

1. An SAE
2. An ADE unless excluded from reporting in Hypoglycemic Events and Hyperglycemic/Ketotic Events sections below
3. An AE occurring in association with a study procedure
4. An AE not related to a study device issue which leads to temporary or permanent discontinuation of the study device
5. An AE that affects the participant's ability to complete any study procedures
6. An AE for which a visit is made to a hospital emergency department
7. Hypoglycemic Events as defined below
8. Hyperglycemia/Ketotic Events as defined

Skin reactions from sensor or pod placement are only reportable if severe and/or required treatment.

For the purpose of this protocol, mild symptoms of hypoglycemia and hyperglycemia (i.e., clinically non-significant) or blood glucose values out of the normal range (whether or not they resulted in delayed meals or correction boluses) will not be reported as AEs unless determined to meet the reportable criteria in the Hypoglycemic Events and Hyperglycemic/Ketotic Events sections below.

All reportable AEs—whether volunteered by the participant, discovered by study personnel during questioning, or detected through physical examination, laboratory test, or other means—will be reported on an AE eCRF.

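### Adverse events in the optional saline Pod trial are reportable for most pump-naive children but not for exempt Dexcom G6 users, who finish it before adverse-event reporting starts

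*Protocol*

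**What the plan says.** Protocol Section 8, under Pump Naïve Users, describes the procedure: "A saline trial consists of wearing a cleared Omnipod® DASH System with the Pod filled with saline to simulate pump therapy". Pump-naive subjects "will have the opportunity to participate in a saline trial during the standard therapy phase", and the protocol adds: "This is optional and not required". The exception is a pump-naive child who is also a current G6 user meeting the CGM criteria. For that child, "the subject will complete the saline trial prior to enrollment in the study".

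Protocol Section 7.1 fixes the enrolment point: "A subject is enrolled in the study upon placement of the first study CGM". SAP Section 2.6 repeats it, and Section 8.1 places it at Visit 2. Section 12.3.2 sets the reporting window: "Adverse event reporting will begin at the start time of the standard therapy phase (i.e., insertion of the CGM sensor"). Conditions or symptoms seen before that time "will not be recorded as an AE and should be collected in the subject's medical history".

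Two other provisions point the other way. Note 2 to the AE definition in Section 12.3.1 brings in events related to any procedure in the investigation plan. The list in Section 12.3.2 makes both SAEs (item 1) and AEs associated with a study procedure (item 3) reportable.

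**The concern.** The saline trial is described in the protocol and uses one device in one way. Whether a bad reaction to it becomes an AE depends on whether the child already had a G6 with enough recent data. That is a difference in data capture with no stated reason behind it.

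What could be lost is a serious event, or a Pod-site reaction that was severe or needed treatment, in a child aged 2 to 5.9 years. Without an AE form it would not come to the Medical Monitor as a reportable event and would not appear in the AE tables. Such events bear on tolerability of the investigational Pod, because Section 2.1.2 says of that Pod that "the patient and fluid contacting components are identical to the DASH Pod". Section 12.1 lists adhesive reaction, infection, ulceration and anaphylaxis among the known Pod risks, so a reportable event is foreseeable.

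**Working it through.** No arithmetic applies, and the plan gives no figure to reproduce. The check is to follow the order of events for two pump-naive children who both choose the saline trial.

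| Step | Not exempt | Exempt G6 user |
|---|---|---|
| Consent and subject ID (7.1) | Visit 1 | Visit 1 |
| Saline trial (8) | During Phase 1, after Visit 2 | Before enrolment |
| Study CGM placed = enrolment (7.1, 8.1) | Visit 2, before the saline trial | Visit 2, after the saline trial |
| AE reporting opens (12.3.2) | Before the saline trial | After the saline trial |
| Severe or treated Pod-site reaction, or SAE, in the trial | AE form | Medical history |
| Child found adhesive-intolerant (exclusion 10) | Already in ITT; exit reason documented | Screen failure; not in ITT |

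Four further readings settle what follows.

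1. **The two rules in Section 12.3.2 pull apart.** Items 1 and 3 would make the event reportable, but the start time removes it for the exempt child. Following the stated start time exactly gives the omission, so this is more than missing detail.

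2. **Medical history is a weak substitute.** Table 1 schedules medical history at Visit 1 only and AE assessment from Visit 2. The saline trial has no row, so no scheduled assessment is tied to it. The Section 7.1 duty to document why a child leaves covers loss of eligibility after standard therapy has begun, not before.

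3. **The tables cover enrolled children only.** This holds for ITT (Protocol 13.3.1, SAP 7.1.1), the safety summaries (SAP 5.4) and the baseline tables (Protocol 13.7, SAP 7.8). An exempt child who reacts and is never enrolled is in none of them.

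4. **The timing is hard to schedule.** Section 7.1 lets MDI subjects who meet the CGM criteria combine Visits 1 and 2. If they do, no interval remains between consent and enrolment for the trial that Section 8 places there. Section 15.4 requires consent before the subject takes part in the study.

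**The case against.** The strongest reply is that very little would be lost. The trial is optional, the device is cleared and the Pod holds saline. Section 12.3.2 makes skin reactions reportable in any phase only if severe or treated, so mild reactions would go unreported after enrolment too. A reaction that worsens after enrolment is reportable if it meets the criteria. Exempt children have also shown at least 80% CGM use over 14 days, which is some evidence, though not proof for the Pod, that they tolerate adhesive. All of this stands, and it is why the point is minor. None of it explains why the same serious or treated reaction should be captured in one group and not in the other.

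A reader might infer several stronger things that the documents do not support.

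- *That these children leave no trace.* Section 7.1 issues a subject ID at consent for use on all source documents and eCRFs, and ineligible children are classed as screen failures. What is missing is an AE record, an explicit duty to record the reaction, and a place in the tables.
- *That the primary safety results by G6 use (SAP 5.4) are biased.* Those endpoints are severe hypoglycemia and DKA in Phase 2, analysed primarily in mITT (SAP 3.1, 7.1.2). A child without a G6 who becomes ineligible in Phase 1 never enters closed loop either, so neither child contributes Phase 2 person-time.
- *That adverse device effects are being missed.* Section 12.3.1 ties that term to an investigational device, and the saline trial uses a cleared one. The event would be an SAE or a study-procedure AE.

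**Conclusion.** The inconsistency is real and its severity is minor. Under the rules as written, a reportable event in the saline trial is an AE for pump-naive children who do the trial in Phase 1. It is not one for those who meet the G6 exemption and do the trial before enrolment. In that subgroup, a child excluded because of the reaction also falls outside the ITT and safety tables.

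The size cannot be estimated. The documents give neither the number of pump-naive exempt G6 users, nor uptake of the trial, nor a rate of reportable Pod reactions. The primary safety endpoints, both effectiveness tests, the alpha allocation and the sample size do not depend on this point. The conclusion assumes that the saline trial counts as a study procedure, which its description in Section 8 supports.

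**What to change.** - **Protocol Section 12.3.2:** start AE reporting, after signed consent, at the earlier of first saline Pod placement or study CGM insertion, for all subjects. Leave the existing reportability rule unchanged, including the threshold for skin reactions.
- **Protocol Section 13.6.1 and SAP Section 5.4:** list pre-enrolment saline-trial AEs, and drop-outs with their reason, separately beside the ITT safety and disposition tables.
- **Enrolment:** keep the single definition at study CGM placement. Making saline Pod placement the enrolment point for this subgroup would create two definitions and change who is in ITT, which is not needed.
- **Protocol Sections 7.1 and 8:** reconcile the option for exempt MDI subjects to combine Visits 1 and 2 with the requirement to finish the saline trial before enrolment, so that consent clearly comes first.

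The cost is an amendment to the wording, a few more AE forms, and slightly more AEs dated before closed-loop start. Because those events are listed separately, the ITT and Phase 2 counts do not change.

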5.2 Study Design

This is a single-arm, multi-center, prospective clinical study. A total of up to 80 children aged 2.0-5.9 years with type 1 diabetes will be enrolled in the study in order to obtain a minimum of 60 evaluable subjects. Subjects will be considered evaluable if they have at least 8-weeks of data during Phase 2.

Subjects will be enrolled across 6-12 clinical study sites. The study schedule consists of the following three phases:

- 1) 14-day outpatient standard therapy phase (Phase 1)
- 2) 13-week outpatient hybrid closed-loop phase (Phase 2)
- 3) Hybrid closed-loop extension phase until the Omnipod 5 System is commercially available (Phase 3)

Figure 3: Study Schedule Timeline

Following subject screening, consenting, system training and enrollment, subjects will commence the standard therapy phase of the study.

Current Dexcom G6 CGM users may provide data from a 14-day period within the last 30-days. The CGM data meeting the minimum criteria must be the most recent data from the last 30-days. For non-G6 users, subjects will wear a study CGM, in blinded mode, to record glucose measurements over 14-days while subjects manage their diabetes at home per their usual routine while wearing a study CGM while remaining on their current MDI or pump therapy, and sensor, if applicable, for 14-days.

After completion of Phase 1 (the standard therapy phase), subjects and/or parents/guardians/caregivers will be trained on the system and transition to Phase 2 (the hybrid closed-loop phase) initiating treatment with the Omnipod Horizon™ System. A subset of subjects (N=40) will participate in activity for a minimum of 3 hours and dietary challenges over the course of 2 consecutive days during Phase 2. Phase 2 will be followed by the extension phase (Phase 3).

Table 1 and Table 3 outline the schedule of assessments for each phase of the study.

Table 1: Schedule of Assessments for Phase 1 and Phase 2

Assessment Schedule	Screening	ST1	ST2	Hybrid Closed-Loop (HCL)											EW ^a
				Phase 1			Phase 2								
Visit Number	1 ^b	2	3	4	5	6	7	8	9	10	11	12	13	UV ^c	
Study Day/Visit Window ^d	-30 to -14d HCL start	-14d to HCL start	-1d to HCL start	1	2 ±1d	3 ±1d	10 ±3d	24 ±3d	38 ±3d	52 ±3d	66 ±3d	80 ±3d	94 ±3d	N/A	
Telephone (T) or Office (O) Visit	O	O	O	O	T/O ^e	T/O ^e	T/O ^e	T/O ^e	T/O ^e	T/O ^e	T/O ^e	T/O ^e	T/O ^e	T/O ^e	O
Laboratory Assessments															
A1C	X (POC & Blood Draw)													X (Blood Draw)	X (Bloo d Draw)

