 - Used to measure sleep disturbance and usual sleep habits
 - IDSS (T1)
 - Used to measure patient satisfaction with their devices and impact on quality of life
 - SUS
 - Used to measure usability of a system
- Training on Glucagon administration and information on treatment of hypo/hyperglycemia

- All subjects and/or parents/guardians are required to have access to glucagon and receive training on how to deliver the medication
- Study device training per manufacturer's instructions (CGM, BG, and ketone meters)
- Dispensing of CGM (blinded for non-G6 users), BG, and ketone meter
- QC testing of BG and ketone meter
 - Must pass as least one level of quality control testing prior to dispensing. QC testing can be done at any time prior to dispensing to the subject.
- CGM sensor placement (Enrollment)
 - Approved anatomical locations for CGM sensor placement will be reinforced as well as the importance of using approved location
- Assessment of activity and routine carb consumption

During this visit, subjects and/or parents/guardians will be dispensed the following supplies:

- Dexcom transmitter
- Dexcom receiver
- Dexcom sensors
- Contour® Next One blood glucose meter
- Contour® Next One blood glucose meter test strips
- Lancets
- Precision Xtra blood ketone meter
- Precision Xtra blood ketone meter test strips

Subjects and/or parents/guardians will be provided, by the site, information regarding treatment of hypoglycemia and hyperglycemia including sick day management and emergency management of severe hypoglycemia and diabetic ketoacidosis. Subjects and/or parents/guardians will be given contact information for study personnel and product support.

If a subject is on MDI, the investigator will advise the subject and/or parent/guardian on the treatment regimen to reduce insulin depending on the insulin action profile of injected doses prior to the commencement of the hybrid closed-loop phase. MDI subjects will be required to keep a MDI Subject Diary to record daily doses of insulin during the standard therapy phase.

8.2 Visit 3

Visit 3 will be conducted in person at the clinical study site up to one (1) day prior to the start of the hybrid closed-loop phase. Visit 3 and Visit 4 may be combined and conducted on the same day. All scheduled assessments will be performed according to Table 1: Schedule of Assessments for Phase 1 and Phase 2. This visit will include:

- Assessment of AEs

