7.4 CALCULATION OF PERCENTAGE OF TIME IN RANGE

Several effectiveness endpoints involve calculation of percentage of time in a specific glycemic range. These endpoints will be based on the direct output from a device (either a CGM or The Omnipod Horizon[™] Automated Glucose Control System). The percentage of time in range (TIR) will be calculated as:

 $100 \times \frac{\# of CGM readings in range}{\# of evaluable CGM readings} = TIR\%$

The following CGM readings will be excluded from analysis, and therefore, from calculation of TIR endpoints:

- No glucose value is provided in the device output, such as due to an error or device deficiency during which the device does not record glucose readings
- CGM readings reported prior to start of standard therapy phase or after subject's discontinuation from HCL

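### For children on injections whose Phase 1 glucose data run up to closed-loop start, the time-in-range comparator can include readings taken after an advised insulin reduction, and the SAP has no rule for them

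*Protocol*

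**What the plan says.** **Phase 1 therapy.** Protocol 5.2 describes non-G6 users as "remaining on their current MDI or pump therapy, and sensor, if applicable, for 14-days". Protocol 8 gives families the instruction "Manage their diabetes at home per their usual routine".

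**Advice to MDI families.** Protocol 8.1 (Visit 2, the start of Phase 1) states that "the investigator will advise the subject and/or parent/guardian on the treatment regimen to reduce insulin depending on the insulin action profile of injected doses", to be done before closed-loop begins. It does not say by how much or how far ahead. The same section has MDI subjects record daily doses in a diary during Phase 1.

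**Comparator window.**
- Non-G6 users: "All non-G6 users will be required to participate in the entire 14-day standard therapy phase" (Protocol 8).
- Extended Phase 1: "If subjects extend beyond the 14-days, the most recent 14-days of data will be used in the endpoint analysis", provided the CGM criteria are met (Protocol 8).
- Current G6 users may supply their own data: "The CGM data meeting the minimum criteria must be the most recent data from the last 30-days" (Protocol 5.2). Whether they qualify is assessed at Visit 1 (Protocol 7.1).
- Visit 3 falls no more than one day before closed-loop start and may be combined with Visit 4 (Protocol 8.2). Closed-loop follows directly on the end of Phase 1 (Protocol 9).

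**Reading exclusions.** SAP 7.4 drops readings that carry no glucose value, and "CGM readings reported prior to start of standard therapy phase or after subject's discontinuation from HCL". It says nothing about days of insulin reduction. Under SAP Section 1, the SAP prevails over the protocol.

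**The concern.** The single-arm design rests its time-in-range comparison on Phase 1 representing usual therapy. A reading taken after an advised insulin reduction does not represent it. Less insulin would be expected to raise glucose, which lowers Phase 1 time in 70-180 and raises Phase 1 time above 180. Both changes would be credited to the device when Phase 2 is subtracted. For time below 70 the direction reverses: a lower Phase 1 value makes an improvement harder to see.

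Three of the four endpoints with formal hypotheses could therefore be shifted, two in favour of the device and one against. The fourth, A1C, has its baseline drawn at screening, before the Visit 2 advice, and is not affected.

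Any effect would fall on MDI children only. It would therefore be concentrated in a comparison by previous pump or CGM use, which SAP 4.3 lists as a possible subgroup. The sponsor intends to submit Phase 2 results for marketing clearance (SAP 2.3), so the size of the estimated gain will be read as well as its p-value.

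**Working it through.** **1. Can the reduction fall inside the window?**

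| Child | Comparator window | Overlap possible? |
|---|---|---|
| MDI, study CGM, Phase 1 not extended | Whole 14-day phase, ending 0-1 day before closed-loop | Yes, because the phase runs up to the start |
| MDI, study CGM, Phase 1 extended | Most recent 14 days | Yes, through the most-recent rule |
| MDI, qualifies on own G6 data at Visit 1 | Earlier 14-day period | Data may predate the Visit 2 advice |
| Already on a pump | Either | No; the advice is for MDI only |

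No rule in SAP 7.4 removes such readings where overlap occurs. A related mismatch follows from SAP 6.4. It takes the Phase 1 insulin comparator at Visit 2, which by Protocol 8.1 covers roughly the preceding 7 days. Insulin and glucose baselines could then describe different regimens in the same child.

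**2. The plan's own figures.** Protocol 13.2.2 and SAP 4.1 assume a mean change of 10 points, SD 10, one-sided 1.25% and 90% power, and state 11 subjects. The normal formula (SD x (z_alpha + z_power) / difference)^2 gives 12.4, so 13. The exact paired t-test gives 16, and 11 subjects give 74% power. The figure 11 does come out of the paired t-test with the feasibility values 13.2 and 10.2. With 60 evaluable subjects planned, this has no practical effect here.

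**3. Size of the bias.** Let k be the days of reduction inside the window, d the time-in-range loss in points on those days, and f the share of subjects affected. None of the three is in the documents; all are assumed.

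- Bias per affected child = k x d / 14
- Study-wide bias = f x k x d / 14

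| Case | k | d | f | Per child | Study-wide |
|---|---|---|---|---|---|
| Low | 1 | 10 | 10% | 10/14 = 0.71 | 0.07 |
| Middle | 2 | 20 | 30% | 40/14 = 2.86 | 0.86 |
| High | 2 | 30 | 30% | 60/14 = 4.29 | 1.29 |

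One to two days is 7-14% of the window. Wider assumptions (k 1-3, d 5-30, f 10-50%) give 0.36-6.4 points per child and 0.04-3.2 study-wide.

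**4. Effect on the test** (paired t, n = 60, SD 10, one-sided 1.25%, noncentral t).
- True gain 10: power is above 99.9%, and still above 99.9% after subtracting 1.29. Subtracting 3.2, the extreme of the wider range, leaves 99.8%.
- True gain zero: the chance of a positive test rises from 1.25% to 1.4% (low), 5.6% (middle) or 10.3% (high).

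**5. Effect of dropping readings on sufficiency.** The criterion is 80% use, or 11.2 of 14 days (Protocol 8.2). From a complete window, dropping 2 days leaves 12, which passes; dropping 3 leaves 11, which fails. A child with 90% use has 12.6 days, and dropping 2 leaves 10.6, which fails. Sufficiency must therefore be judged before any exclusion.

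**The case against.** A reader might infer that Phase 1 does contain reduced-insulin days for children on injections generally, and that the reported gain is therefore overstated. The documents do not show that:

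- Protocol 8.1 gives no start, length or size of the reduction. Tying it to the action profile of injected doses also fits an adjustment of only the last dose or doses, so the overlap could be hours.
- The most-recent-14-days rule applies only when Phase 1 is extended. It does not move everyone's window to the final days.
- MDI children who qualify on their own G6 data can contribute readings from before the advice.
- The bias is not one-directional: time below 70 moves against the device, and baseline A1C is untouched.
- Study success rests on rates of severe hypoglycemia and DKA (SAP 2.4), the primary effectiveness endpoints carry no labeling claims (SAP 4.2), and subgroup analyses are optional (SAP 4.3).

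All of this stands. It limits the point to a possible and probably small bias in part of the cohort. It does not remove the contradiction between Protocol 5.2 and 8 on one side and 8.1 on the other, or the absence of any analysis rule. An unextended study-CGM window still reaches to within a day of closed-loop start.

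A practical objection also stands in part. The diary records daily doses, but nothing says it marks when an advised reduction began, and a lower dose alone does not identify one. The date may need a separate site entry.

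**Conclusion.** The point holds in limited form. For MDI children whose Phase 1 CGM data run up to closed-loop start, following the plan as written can put readings taken off usual therapy into the time-in-range comparator. Overlap is possible, not shown.

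The likely direction is a modest overstatement of the improvement in time 70-180 and time above 180, and an understatement for time below 70. On assumed inputs of 1-2 days, a 10-30 point loss and 10-30% of subjects affected, the bias is 0.7-4.3 points per affected child and about 0.1-1.3 points study-wide, against a planned 10.

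It matters for the size of the estimate and for any prior-MDI subgroup. It does not threaten significance at the planned effect or the safety-based success criterion. Type I error would be raised only if the true gain were near zero. This is a cheap improvement, not a flaw that undermines the trial.

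**What to change.** - In SAP 7.4, add that for MDI subjects Phase 1 CGM readings from the first advised reduced dose onward are excluded from Phase 1 time-in-range calculations, with the date taken from the MDI diary or a site record.
- Apply the 80% use and 2,016-value criteria to the full Phase 1 window, before this exclusion, so that no child is lost because of it.
- Report a sensitivity analysis with those readings included.
- Reconcile Protocol 5.2, 8 and 8.1, so that the description of Phase 1 as current therapy and usual routine acknowledges the advised reduction.

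The cost is a few sentences, one extra analysis and, where the diary does not identify the date, one site-recorded date per MDI child. Under the assumption above, affected children lose one or two days of Phase 1 readings. No change to the transition itself is proposed.
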